| 
Study objectives
 | 
 ● To describe the characteristics of COVID-19 and its sequelae in several types of fragile populations. ● To describe the rate, the etiology (SARS-CoV-2 variants), the severity of COVID-19, and the rate of re-infections in several types of fragile patients. ● To evaluate the immunologic response to the COVID-19 vaccination in selected fragile populations. ● To evaluate the safety of COVID-19 vaccination in selected fragile populations. |

| | |
|--------------------|--|
| | 
 Identify human genetic markers and epigenetic characteristics in frail patients during post-vaccination monitoring and in case of breakthrough infections as well as to analyse the gut microbiome in such patients |
| Study population | Patients of all age and any comorbidity included in an ORCHESTRA fragile population cohort |
| Inclusion criteria | 
 Any age Any comorbidity Person (or attorney or deputy who has been authorized to make the decision for patients who lack capacity) consent to participate or appropriate local waiver of consent. |
| Exclusion criteria | Patients did not agree to participate. |
| Study design | 
Multicenter, multinational observational study aimed at building several types of fragile populations in which to assess the rate and the clinical spectrum of COVID-19, with particular interest in long-term follow-up, and at monitoring clinical and immunological response after SARS-CoV-2 vaccination in fragile subjects.
 
For long-term follow-up of fragile patients with COVID-19, a predefined schedule of assessment is planned in alignment with Work Package (WP) 2. Patients already diagnosed with COVID-19 can be included if baseline data according to WP2 protocol have been collected, and if follow-up visits are possible.
 
For assessing the clinical and immunological response to vaccination, patients will be prospectively evaluated at baseline (first and
 |

| | |
|--------------------|---|
| | second vaccination doses), and at multiple timepoints after vaccination with clinical and immunological assessments. |
| Vaccines | Approved COVID-19 vaccines |
| Follow-up | Patients will be followed-up for up to 18 months after the SARS-CoV-2 infection diagnosis or up to 12 months after vaccination. |

3.2 Schedule of assessments (SoA)

Table 1. Schedule of assessments for long-term follow-up in COVID-19 patients.

| | COVID-19 (2 weeks ¹ ± 2 weeks) | 3 months ¹ (± 1 month) | 6 months ¹ (± 1 month) | 12 months ¹ (± 2 months) | 18 months ¹ (± 3 months) |
|--|---|--------------------------------------|--------------------------------------|--|--|
| Screening/baseline | | | | | |
| Inclusion criteria ¹ | X | | | | |
| Demographics ² | X | | | | |
| Healthcare setting ³ | X | | | | |
| Length of hospital stay, days | X | | | | |
| ICU admission | X | | | | |
| Medical history ⁴ | X | | | | |
| Treatment | | | | | |
| Comorbidity management ⁵ | X | X | X | X | X |
| Anti-COVID therapy ⁶ | X | | | | |
| Antibiotic therapy | X | X | X | X | X |
| Oxygen therapy ⁷ | X | X* | X* | X* | X* |
| SARS-CoV ² ⁸ and other respiratory pathogen vaccination ⁹ | X | X | X | X | X |
| Clinical assessment | | | | | |
| Relevant medical new events ¹⁰ | X | X | X | X | X |
| COVID-19 symptom ¹¹ onset | X | | | | |
| COVID-19 symptom end | X | X* | X* | X* | X* |
| COVID severity ¹² | X | | | | |
| SOFA score | X | | | | |
| Vital signs ¹³ | X | X | X | X | X |
| Physical examination ¹⁴ | X | X | X | X | X |
| 12-lead electrocardiography | X | X | X | X | X |
| 6-minute walking test | X | X | X | X | X |
| DLCO (diffusing capacity for carbon monoxide) | X | X | X | X | X |
| Pulmonary function test ¹⁵ | X | X | X | X | X |
| Questionnaires | | | | | |
| Functional status ¹⁶ | X | X | X | X | X |
| Respiratory impairment ¹⁷ | X | X | X | X | X |
| Mental health ¹⁸ | X | X | X | X | X |
| Risk perception and behaviour^{19, 20} | | | | | |
| SARS-CoV-2 vaccination: acceptance/non-acceptance and reasons ²¹ | | X | | X | X |
| Socio-economic indicators | | X | | X | X |
| Use of resources (COVID-19 unrelated) | | X | | X | X |
| Imaging | | | | | |
| Lung ultrasound | X | X | X* | X | X* |
| X-ray | X | X | X* | X* | X* |
| High-resolution CT scan | X | X | X* | X* | X* |
| Cardiac ultrasound | X | X | X* | X | X* |
| Cardiac MRI ²² | X ²¹ | X ²¹ | X* | X ²¹ | X* |
| Biochemistry | | | | | |

| | | | | | |
|---|---|-------------------|-------------------|-------------------|----|
| Blood tests ²³ | X | X | X* | X | X* |
| Arterial blood gas test (pO ₂ /pCO ₂ /pH) | X | X | X* | X* | X* |
| Urine tests ²⁴ | X | X | X* | X | X* |
| Immunology | | | | | |
| Immune - serology and type I IFNs autoantibodies | X | X | X | X | X |
| Immune - cytokine and chemokine | X | X ³⁵ | X ³⁵ | X ³⁵ | X* |
| Immune - cellular | X | X ³⁵ | X ³⁵ | X ³⁵ | X* |
| Microbiological tests-NP swabs | | | | | |
| Viral variant and metagenomics sequencing | X | X*, ³⁴ | X*, ³⁴ | X*, ³⁴ | X* |
| EDTA whole blood | | | | | |
| Genetic and epigenetic analysis | X | X | X | X | X |
| Stool Sample (faeces or rectal swab) | | | | | |
| Metagenomic sequencing | X | | X | | X |
| Microbiological tests | | | | | |
| SARS-CoV-2 molecular test in nasopharyngeal swab or tracheal aspirate or bronchoalveolar lavage or saliva | X | X* | X* | X* | X* |
| Adjunctive variables for specific fragile populations | | | | | |
| HIV | | | | | |
| HIV-infection status ²⁵ | X | X | X | X | X |
| HIV-Infection therapy ²⁶ | X | X | X | X | X |
| Assessment of adherence to follow-up visits and antiretroviral therapy | X | X | X | X | X |
| Elderly | | | | | |
| Cognitive status ²⁷ | X | X | X | X | X |
| Pregnant women/new born | | | | | |
| History of positive SARS-CoV-2 molecular test on amniotic fluid or breast milk ²⁸ | X | | | | |
| History of detection of microthrombotic disease on placenta tissue or umbelical cord tissue | X | | | | |
| Children | | | | | |
| History of positive SARS-CoV-2 molecular test on amniotic fluid or breast milk ²⁹ | X | | | | |
| Biometric paramethers ³⁰ | X | X | X | X | X |
| Transplant | | | | | |
| Transplant general information ³¹ | X | | | | |
| Graft function ³² | X | X | X | X | X |
| Immunosuppressive regimen ³³ | X | X | X | X | X |

| Onco-haematology | | | | | |
|---|---|---|---|---|---|
| Assessment of adherence to oncologic follow-up visits and therapy | X | X | X | X | X |
| Assessment of progression of the disease and relapse | X | X | X | X | X |
| Assessment of adverse events ³⁴ | X | X | X | X | X |

Footnotes

Modular data capture according to level of commitment (level I, level II, level III).

| | |
|-----------------|--|
| Level I | Assessments in level I are mandatory |
| Level II | Customized according to the feasibility of each cohort |

* Reassessed only if outside the normal ranges at the previous assessment or if clinically indicated

1. Day 0: first positive SARS-CoV-2 test
2. Demographics: age (years), sex, ethnic group (African, Asian, European, Latin America...), education (no formal education, lower than college, college or higher), cigarette smoking (never-smoker, former smoker, current smoker), usual residence (home, long-term care facility, public dormitory, prison, homeless), current occupation (student, unemployed with no benefits, unemployed with benefits, employed, self-employed, informal worker)
3. Healthcare setting: (a) outpatient (b) non-intensive care unit (c) intensive care unit.
4. Medical history: cardiovascular diseases (hypertension, coronary artery disease, congestive heart failure), diabetes (without insulin, with insulin), chronic respiratory disease (asthma, chronic obstructive pulmonary disease, obstructive sleep apnoea, restrictive lung disease, pulmonary hypertension), kidney disease (chronic with/without dialysis), liver disease other than cancer (HBV/HCV/HDV chronic viral hepatitis, other chronic disease, cirrhosis), metabolic disease, immunosuppressive conditions (solid organ transplant recipient, auto-immune diseases), cancer (solid cancer, haematological malignancies, type of primitive cancer/haematological malignancies, presence of metastases, if ongoing chemotherapy), mental or neurological disorders (psychiatric illness, anxiety disorder, mood disorder, psychotic disorder, Alzheimer disease, dementia other than Alzheimer, Parkinson's disease, myasthenia gravis, epilepsy, stroke (with/without residual deficits, neuromuscular disease, multiple sclerosis), muscular dystrophy, amyotrophic lateral sclerosis); TB co-infection; other opportunistic co-infection (specify) for HIV population
5. Comorbidity management: drug name and dose (to include only treatments taken regularly)
6. Anti-COVID therapy: drug name, maintenance dose, and duration

7. Antibiotic therapy: drug name, dose, duration, and type of treated infection
8. Oxygen therapy: nasal prongs, face mask, face mask with reservoir, high-flow nasal cannula, non-invasive ventilation, mechanical ventilation; numbers of O₂ (L/min) provided (maximum reached) and fraction of inspired O₂ (FiO₂) provided (maximum reached)
9. SARS-CoV-2 vaccination: vaccine name, date of administration
10. Relevant new medical events or worsening of previous conditions, including deep venous thrombosis, pulmonary embolism, infections (including a new SARS-CoV-2-infection during follow-up), malignancies (type of cancer, overall stage).
11. Symptoms: abdominal pain, ageusia/dysgeusia, anosmia, balance impairment, behaviour disorder, chest pain or chest tightness, confusion, cough, delirium, diarrhoea, disrupted sleep, dizziness, dyspnoea, fatigue, fever (including low-grade fever), headache, hypothermia, impaired cognitive status, lethargy, loss of appetite, mood affective disorder, myalgia, nausea/vomiting, palpitation, phlegm, runny nose, sore throat, stuffed nose, syncope, wheeze.
12. WHO Clinical Progression Scale
13. Vital signs: dead/alive, blood pressure, body temperature, heart rate, respiratory rate, peripheral oxygen saturation
14. Physical examination: BMI, abdominal examination, pulmonary examination, cardiac examination, neurological examination, peripheral vascular examination
15. Pulmonary function test: FEV₁, FVC, FEV₁/FVC, TLC, FRC, RV
16. Questionnaires to address the functional status: Post-COVID-19 Functional Status (PCFS) Scale, Global Physical Activity, Questionnaire (GPAQ), Barthel Index, Medical Outcome Study Short Form (MOS SF)-36 Score, EuroQol five-dimension five-level (EQ-5D-5L) questionnaire, Clinical Frailty Scale (CFS), Basic Activity of Daily Living (BADL).
17. Questionnaires to address the respiratory impairment: Saint George Respiratory Questionnaire (SGRQ), Transition Dyspnoea Index (TDI), mMRC (Modified Medical Research Council) Dyspnea Scale
18. Questionnaires to address the mental health: Hospital Anxiety and Depression Scale (HADS), Kessler Psychological Distress Scale (K10), Impact of Event Scale – Revised (IES-R), Resilience Scale for Adults (RSA)
19. Perceived risk of re-infection on a scale 0-10 (no risk- very high risk); perceived risk of admission/re-admission on a scale 0-10 (no risk- very high risk)
20. Frequency mask-wearing (type of mask); frequency hand washing; respect of social distance; avoidance of social gathering

21. Was the vaccine accepted? Why not accepted (lack of trust in efficacy and/or safety; not useful in the specific case; prefer someone else gets it before me)
22. Cardiac MRI only if abnormal cardiac ultrasound
23. Blood tests: White blood cell count, lymphocyte count, neutrophil count, platelets, sodium, potassium, creatinine, glucose, bilirubin, alanine aminotransferase, aspartate aminotransferase, gamma glutamyl transpeptidase, albumin, lactate dehydrogenase, ferritin, creatine kinase, fibrinogen, INR, partial thromboplastin time, D-dimer, NT-pro-BNP, troponin, C-reactive protein (CRP), procalcitonin, venous lactate
24. Urine tests: pH, concentration, protein, glucose, red blood, white blood cell count
25. CD4 lymphocyte count; HIV-viral load; AIDS status
26. HIV-therapy: drug name and dose (only ongoing treatment); previous switch to other regimens for virological failure
27. Questionnaires to address cognitive status: Cognitive Failure Questionnaire (CFQ), Mini-Mental State Examination, Clinical Dementia rating Scale, Montreal Cognitive Assessment (MOCA).
28. Results of SARS-CoV-2 molecular test on amniotic fluid
29. Weight, height/length, cranial circumference, BMI
30. Type of transplant (heart, lung, kidney, liver, pancreas); single-combined; year of transplantation
31. Graft function: good, impaired, failure, rejection acute-chronic, recurrence of underlying disease, other
32. Immunosuppressive regimen: drug name and dose
33. According to Common Terminology Criteria for Adverse Events (CTCAE)
34. At least one of three timepoints (month 3, month 6, month 12) is required to perform metagenomics analysis.
35. At least one of the three timepoints (month 3, month 6, month 12) is required.

Table 2. Schedule of post-vaccination assessments

| | 1 st dose | 2 nd dose ² | 3 months (± 1 month)* | 6 months (± 2 months)* | 12 months (± 3 months)* |
|--|----------------------|-----------------------------------|--------------------------|---------------------------|----------------------------|
| Baseline information¹ | | | | | |
| Underlying fragile condition | X ¹ | X ¹ | | | |
| Healthcare setting (i.e. LTCF) | X ¹ | X ¹ | | | |
| Comorbidities | X ¹ | X ¹ | | | |
| Concomitant medical treatments | X ¹ | X ¹ | | | |
| Past and/or new COVID-19 disease ³ | X ¹ | X ¹ | X | X | X |
| Clinical evaluation | | | | | |
| Relevant medical new events ⁴ | X | X | X | X | X |
| Clinical symptoms suggestive of COVID-19 | X | X | X | X | X |
| Lab assessment | | | | | |
| Whole blood count | X | X | | | |
| CD4/CD8 count | X | X | | | |
| IgG level | X | X | | | |
| C3 level | X | X | | | |
| Immunology | | | | | |
| Immune - serology and type I IFNs autoantibodies | X | X | X | X | X |
| Immune - cytokine and chemokine | X | X ⁷ | X ⁷ | X ⁷ | X ⁷ |
| Immune - cellular | X | X ⁷ | X ⁷ | X ⁷ | X ⁷ |
| Microbiological tests-NP swabs | | | | | |
| Viral variant and metagenomics sequencing | X ⁵ | X ⁵ | X ⁶ | X ⁶ | X ⁶ |
| EDTA whole blood | | | | | |
| Genetic and epigenetic analysis | X | | X | X | X |
| Stool Sample (faeces or rectal swab) | | | | | |
| Metagenomic sequencing | X | | X | | |
| Questionnaires¹ | | | | | |
| Risk perception and behavior | X ¹ | | | X | X |
| Socio-economic indicators | X ¹ | | | X | X |
| Use of resources (COVID-19 unrelated) | X ¹ | | | X | X |
| Adverse Events dedicated questionnaire | | X | X | X | X |
| Immune response | | | | | |
| Quantitative Ab anti-S IgG ⁵ | X | X | X | X | X |
| Qualitative Ab anti-N IgM+IgG ⁵ | X | | | | |
| Anti-SARS-CoV-2 sero-neutralization | X | X | X | X | X |
| Cytokine / chemokines | X | X | X | X | X |
| Anti-SARS-CoV-2 cell immunity | | X | | X ⁶ | X ⁶ |

Footnotes

Modular data capture according to level of commitment (level I, level II).

| | |
|----------|---|
| Level I | Assessments in level I are core and should be prioritized |
| Level II | Customized according to the feasibility of each cohort |

*3, 6 and 12 months counted from the 1st dose.

¹For centers able to follow patients since the administration of the first and second vaccination doses the baseline information and the risk perception behavior should be collected at one of these time-points, in the other cases such information should be collected during the first post-vaccination follow-up.

²The assessment at 2nd dose is mandatory in patients who will receive such dose within 8-12 weeks after first dose (current AstraZeneca vaccination schedule).

³If COVID-19 diagnosis, assessments reported in Table 1 are required.

⁴Relevant new medical events or worsening of previous conditions, including new malignancies (type of cancer, overall stage, Kaposi skin-visceral, Lymphoma localization-type, Leukemia lymphoid-myeloid acute-chronic), deep venous thrombosis, pulmonary embolism, infections (including a new SARS-CoV-2-infection during follow-up)

⁵At least one time-point at 1st and 2nd dose is required.

⁶At least one of the three timepoints (month 3, month 6, month 12) is required.

⁷At least one of the four timepoints (2nd dose, month 3, month 6, month 12) is required.

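### Table 1 records the listed COVID-19 symptoms with an onset only at the 2±2-week visit, so listed symptoms that start late or return have no dated field during the 18-month follow-up

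*Protocol*

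**What the plan says.** Table 1 in Section 3.2 of the protocol sets the follow-up of infected patients at 2 weeks (±2 weeks) and at 3, 6, 12 and 18 months. Two of its rows concern symptoms.

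- The row "COVID-19 symptom ¹¹ onset" carries footnote 11, a list of 30 symptoms. It has one mark, at the first visit. The four later cells are blank.
- The row "COVID-19 symptom end" is marked at the first visit and then carries a starred mark at each of the four later visits. The asterisk is defined as "Reassessed only if outside the normal ranges at the previous assessment or if clinically indicated".

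The row for new medical events is unstarred at all five visits. Its footnote 10 reads "Relevant new medical events or worsening of previous conditions, including deep venous thrombosis, pulmonary embolism, infections (including a new SARS-CoV-2-infection during follow-up), malignancies" and adds details of the cancer; it names no individual symptom. Table 2, the post-vaccination schedule, has a row "Clinical symptoms suggestive of COVID-19" marked without condition at every visit.

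The first objective in the synopsis is "To describe the characteristics of COVID-19 and its sequelae in several types of fragile populations". Section 12 lists reinfection and/or clinical relapse among the endpoint variables.

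**The concern.** The long-term follow-up is meant to describe what happens after the acute illness. Under Table 1 the symptom list is opened once, within about four weeks of the first positive test, and afterwards the symptom rows can only close entries. A patient without palpitation or headache at the first visit has no later line on which either would be entered with a date. A symptom that resolved and then returned has no line on which it can be reopened.

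At stake are the description of sequelae, the description of clinical relapse, and any comparison of symptom courses built on these rows between fragile groups whose acute illness differs. Section 6 notes that asymptomatic or mild disease is often reported in pregnant women and children. For groups like these, later entries in the two rows would partly reflect how the acute illness presented. No analysis plan can repair this, because an onset that was never collected cannot be recovered.

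**Working it through.** **1. Reading the schedule.** The protocol states no symptom rate, sample size or power for symptoms, so there is no figure to reproduce. The two rows side by side:

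| Row | 2±2 wk | 3 mo | 6 mo | 12 mo | 18 mo |
|---|---|---|---|---|---|
| Symptom onset (footnote 11) | X | – | – | – | – |
| Symptom end | X | X* | X* | X* | X* |

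For a given symptom and patient, these rows allow the change from present to absent but not from absent to present. In a fixed set of patients the recorded prevalence is therefore non-increasing. The clinical-indication limb of the asterisk does not change this, because the row it reopens records an end, not an onset.

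**2. What other assessments pick up.**

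- Breathlessness and other respiratory impairment: SGRQ, TDI, mMRC and lung function, unstarred at every visit.
- Mood, distress and function: the mental-health and functional-status questionnaires, unstarred at every visit.
- Sleep, concentration, effort and appetite: items of the CES-D in Annex 2, tagged for baseline and follow-up and required of all patients by Section 11.
- Cognition: dedicated tests at every visit, listed for the elderly only.
- New SARS-CoV-2 infection: the new-events row.
- Anosmia, ageusia, palpitation, headache: no dedicated item in the later columns of Table 1 or in Annex 2. Annex 3 lists headache and tachycardia, but as events after a vaccine dose.

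None of these routes repeats the footnote 11 list with onset dates.

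**3. Illustration of size (all rates assumed).** Let r be the share of symptoms that resolve per visit interval and q the share of symptom-free patients with new or returning symptoms per interval, over four intervals.

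- Recorded: p(t) = p(t−1)·(1−r)
- True: p(t) = p(t−1)·(1−r) + [1−p(t−1)]·q

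With a starting prevalence of 60%, r = 30% and q = 5%:

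- Recorded: 60.0, 42.0, 29.4, 20.6, 14.4%
- True: 60.0, 44.0, 33.6, 26.8, 22.4% (first step: 0.60×0.70 + 0.40×0.05 = 0.44)
- Share missed at 18 months: 1 − 0.144/0.224 = 36%

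Share of symptoms present at 18 months that the two rows miss:

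| Start | r | q=0 | q=2% | q=5% | q=10% |
|---|---|---|---|---|---|
| 30% | 30% | 0 | 36% | 58% | 72% |
| 30% | 50% | 0 | 64% | 81% | 89% |
| 60% | 30% | 0 | 19% | 36% | 51% |
| 60% | 50% | 0 | 45% | 66% | 79% |

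The model applies the same r and q to intervals of unequal length and ignores the partial cover in step 2. It shows direction and sensitivity and is not an estimate for this study.

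**4. The fixed-set condition.** Suppose prevalence in the whole cohort falls from 30% to 27% (0.30×0.9), and 90% of symptomatic but only 70% of symptom-free patients attend. Prevalence among attendees is 0.27×0.9 / (0.27×0.9 + 0.73×0.7) = 0.243/0.754 = 32%. With 50% attendance among the symptom-free it is 0.243/0.608 = 40%. Observed prevalence can therefore rise through selective attendance, although no patient's record can.

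**The case against.** The strongest case on the other side is that Table 1 follows sequelae mainly by other means. Physical examination, ECG, walking test, diffusing capacity, lung function and the functional, respiratory and mental-health questionnaires are unstarred at every visit. Annex 2 asks again about sleep, concentration and effort. The asterisk rule leaves room for clinical judgement, and footnote 10 is open-ended, since its examples follow the word including. Section 12 names no symptom-prevalence endpoint; it measures change in condition by functional questionnaire or by parameters of the underlying disease. The contrast with Table 2 is also weaker than it looks, because its symptom question may serve to detect infection after vaccination. Finally, the eCRF is not shown and might hold the missing field.

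Much of this stands, and it rules out three stronger readings that a reader might infer:

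- That sites never ask about later symptoms, or that late sequelae count as zero in patients symptom-free at first. The unstarred assessments can detect later breathlessness, low mood or functional loss in such patients.
- That symptom prevalence can only fall. This holds only for the two rows in a fixed set of patients.
- That comparisons of sequelae between fragile groups are biased in general. Only comparisons built on these two rows are affected, and Section 6 speaks of asymptomatic or mild disease, so many of those patients may have symptoms recorded at the first visit.

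What the objection does not answer is the gap itself. No scheduled assessment repeats the list with dates, an open-ended events row is no substitute for a checklist, and several listed symptoms have no other route.

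**Conclusion.** The point holds in a limited form. As written, Table 1 gives late-onset or returning footnote 11 symptoms no dedicated, dated field after the first visit, and prevalence from the onset and end rows cannot rise in a fixed set of patients. Some domains are partly covered elsewhere; others, such as anosmia, ageusia, palpitation and headache, are not. This weakens the description of sequelae and of clinical relapse. Reinfection is less affected, since the new-events row names it.

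The size is unknown because the protocol gives no rates. Under the assumed grid (start 30–60%, resolution 30–50%, late onset or relapse 2–10% per interval), the two rows alone miss 19–89% of symptoms present at 18 months. With no late onset or relapse they miss none. The conclusion rests on the protocol text; an eCRF that already repeats the list would remove the loss in practice but not the gap in the schedule. It is a cheap improvement rather than a flaw that undermines the study.

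**What to change.** In Table 1, mark the footnote 11 checklist as an unstarred X at 3, 6, 12 and 18 months for every infected patient, including those symptom-free at the first visit. For each symptom, record presence or absence with onset and end dates. Report persistent, relapsing and new-onset symptoms separately.

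The cost is one changed row and an existing eCRF page repeated at visits already planned: a few minutes per visit, feasible also at the virtual assessments that Section 11 allows in some cohorts, such as the children's. The downside is that some recorded symptoms will be unrelated to COVID-19.

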11. STUDY PROCEDURES

In Figure 1, a study work flow is shown.

Figure 1: study work flow

All included patients will be evaluated during the scheduled visits for the underlying condition. During such visits, the following actions are required:

- Distribution of a questionnaire to capture the impact of COVID-19 pandemic on the socio-economic indicators, on the access to health care services, and to investigate risk perception and behavior towards preventing infection and COVID-19 disease, including vaccine acceptance. This questionnaire should be administered at two different time-points with an interval of at least 6 months to capture changes in behavior over the study period (Annex 1a or Annex 1b in case of children cohorts).

- Distribution of psychological scale questionnaires to investigate the impact of lockdown measures on mental health (Annex 2).
- Screening for past and/or current COVID-19 disease by medical interview, serology determination and nasopharyngeal swab or saliva specimens' collection.
- Collection, processing and storage of plasma for cytokine and chemokine analysis.
- Collection, processing and storage of serum for the subsequent sero-neutralization and type I IFNs autoantibodies detection.
- Collection, processing and storage of PBMCs for the subsequent anti-COVID-19 cellular immunity analysis.
- Collection, processing and storage of whole blood for genetic and epigenetic analysis.
- Collection, processing and storage of nasopharyngeal samples for SARS-CoV-2 detection and variant identification if clinically relevant.
- Collection, processing and storage of stool samples for metagenomic sequencing.
- In immunocompromised fragile cohorts, laboratory tests to assess the baseline “net state of immunosuppression” including whole blood count, lymphocyte differentiation, immunoglobulin levels, and complement (C3) levels should be done at the baseline (first clinical evaluation).

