12. STUDY VARIABLES

Endpoint variables:

- Infection with SARS-CoV2 detected by RT-PCR on respiratory/saliva specimens;
- Reinfection and/or clinical relapse defined according to recent proposed definitions (7);
- Clinical spectrum of COVID-19 according to WHO mild, moderate, severe, and critical criteria (<https://www.who.int/publications/i/item/WHO-2019-nCoV-clinical-2021-1>);
- Duration of viable viral shedding in fragile patients diagnosed with COVID-19;
- Immune response in patients diagnosed with and/or vaccinated against COVID-19 assessed according to study protocol procedures (see above);
- All-cause mortality during the follow-up period;
- Change in basal clinical condition assessed by questionnaire on functional status and/or according to specific parameters of underlying fragile condition (i.e. graft function, cancer stage etc).

Baseline variables will include:

- Demographic data (sex, date of birth, ethnicity, blood group);
- Underlying conditions;
- Vaccination status against respiratory infectious diseases (i.e. Influenza, pneumococcus, BCG) if available.

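### Table 1 and Section 11 are not reconciled on whether previously infected patients are tested routinely or only when indicated; where Table 1 alone is followed, symptom-free reinfection is under-detected.

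*Protocol*

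**What the plan says.** In Table 1 (Section 3.2), which schedules follow-up after a SARS-CoV-2 diagnosis, the row "SARS-CoV-2 molecular test in nasopharyngeal swab or tracheal aspirate or bronchoalveolar lavage or saliva" carries a plain X at the COVID-19 visit and an X with an asterisk at months 3, 6, 12 and 18. The asterisk is defined as "Reassessed only if outside the normal ranges at the previous assessment or if clinically indicated".

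Section 11 states that "All included patients will be evaluated during the scheduled visits for the underlying condition" and lists actions required at those visits. One is "Screening for past and/or current COVID-19 disease by medical interview, serology determination and nasopharyngeal swab or saliva specimens' collection". A separate item in the same list concerns "nasopharyngeal samples for SARS-CoV-2 detection and variant identification if clinically relevant". Section 8 says that every cohort mixes patients with and without past or new infection. Section 11 then asks for the Table 1 follow-up in infected patients, and footnote 3 of Table 2 requires the Table 1 assessments after a COVID-19 diagnosis. Neither place says whether the routine screening goes on.

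The synopsis lists "the rate of re-infections in several types of fragile patients" among the objectives. Section 12 makes RT-PCR-detected infection an endpoint and adds "Reinfection and/or clinical relapse defined according to recent proposed definitions".

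**The concern.** For a previously infected patient with no symptoms and a negative last test, Section 11 asks for a swab or saliva specimen and Table 1 asks for none. A site can defend either course. If it follows Table 1, testing becomes less intensive just when the patient becomes at risk of reinfection, and symptom-free reinfections are lost that a routine swab might have caught.

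Because infection is defined by RT-PCR, the case count depends on who is swabbed. The described reinfection rate would then be too low by an unknown amount. With 29 cohorts in 14 countries (Section 9), the shortfall could differ between sites, so a difference in reinfection rates between fragile populations could partly reflect testing practice. Section 7 also plans to study predictors of infection, and Section 13 allows Cox models with time-dependent covariates. If prior infection entered such a model, lighter testing after the first episode would push its estimated effect towards protection.

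**Working it through.** The protocol gives no figure on this point, so there is nothing to reproduce. The check is textual, followed by an illustration of size on assumed inputs.

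**Text**

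1. Who is screened: Section 11 covers all included patients, and Section 8 makes the previously infected part of them. Read literally, they stay under routine screening.
2. What Table 1 orders: a repeat molecular test only on a previous abnormal result or a clinical indication.
3. How the two combine: not stated in Section 11 or in Table 2, footnote 3.
4. Whether other Table 1 rows close the gap:
   - The new-medical-events row is unconditional and names new SARS-CoV-2 infection, but it records events and orders no test.
   - Serology is unconditional, but the infection endpoint is RT-PCR and the protocol gives no serological rule for reinfection.
   - Footnote 34 asks for at least one nasopharyngeal time point among months 3, 6 and 12 for metagenomics, but those cells also carry the asterisk.

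   These rows narrow the gap without closing it.

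**Size if Table 1 replaces Section 11**

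All inputs are assumptions except the 18-month follow-up and its four time points.

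- s = share of infections that prompt a test under either rule. A symptom-free share of 20-40% gives s = 0.8 to 0.6.
- V = routine swabs in 18 months (548 days). Section 11 gives no visit frequency. V = 4 borrows the Table 1 time points; V = 18 stands for monthly visits.
- w = days PCR-positive: 7, 14 or 28.
- d = min(1, V × w / 548), the chance that a routine swab falls in the positive window.
- Ratio of infections found, conditional over routine testing: R = s / (s + (1 − s) × d). Shortfall = 1 − R.

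Lowest case at V = 4: d = 4 × 7 / 548 = 0.051; R = 0.8 / (0.8 + 0.2 × 0.051) = 0.987; shortfall 1.3%.

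Highest case at V = 4: d = 4 × 28 / 548 = 0.204; R = 0.6 / (0.6 + 0.4 × 0.204) = 0.880; shortfall 12.0%.

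| V | w (days) | d | Shortfall, s = 0.8 | Shortfall, s = 0.6 |
|---|---|---|---|---|
| 4 | 7 | 0.051 | 1.3% | 3.3% |
| 4 | 14 | 0.102 | 2.5% | 6.4% |
| 4 | 28 | 0.204 | 4.9% | 12.0% |
| 18 | 7 | 0.230 | 5.4% | 13.3% |
| 18 | 14 | 0.460 | 10.3% | 23.5% |
| 18 | 28 | 0.920 | 18.7% | 38.0% |

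Ceiling: if routine swabs caught every symptom-free infection (d = 1), R = s and the shortfall would be 20-40%. Floor: if Section 11 screening continues after infection at the same visits, R = 1 and the shortfall is zero.

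**The case against.** The strongest reply is that the two schedules are additive. Section 11 concerns visits for the underlying condition, and Table 1 concerns visits timed from the first positive test. Nothing says one displaces the other, so reinfection is sought routinely as well and no bias arises. This is a fair reading, and it defeats any claim that reinfection must look rarer by construction. It does not show that sites will read the protocol that way, because Section 11 presents Table 1 as the detailed visit schedule for infected patients and the table itself says a repeat test is done only on a condition.

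A second reply is that routine detection before infection is itself weak. No swab frequency is given, and the further Section 11 item on nasopharyngeal samples has a clinical-relevance qualifier that may cover detection as well as variant identification. Many first infections are past diagnoses recorded from February 2020, and some cohorts (Sections 9.8.2 to 9.8.4) enter patients through hospital care for confirmed or suspected COVID-19. None of those first infections was found by Section 11 swabs. This stands, and it confines the contrast to first infections detected prospectively.

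Third, Section 13 specifies no comparison of first infection with reinfection and does not name prior infection as a predictor. That stands too: bias in such a comparison is conditional on its being made. An understated and site-dependent reinfection rate does not need the comparison.

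Finally, the cited reinfection definition is not reproduced in the protocol, so whether a symptom-free positive would count cannot be checked here. If it would not, the gap matters less.

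**Conclusion.** The point holds as an unreconciled testing rule with a conditional consequence. The protocol does not say whether routine screening continues after a first infection. Where a site lets Table 1 replace it, symptom-free reinfection is under-ascertained relative to prospectively detected first infection, and ascertainment may vary by site.

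The documents do not determine the size. It is zero if Section 11 screening continues; about 1-12% with four swabs in 18 months, a 7-28 day positive window and 20-40% symptom-free infections; and about 5-38% with monthly swabs on the same assumptions. The calculation also assumes that symptom-prompted testing works equally well before and after a first infection and that swab dates are unrelated to infection.

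A reader might infer that the design builds in a spurious 20-40% protection from prior infection. The documents do not support that. It would need Table 1 to displace Section 11 everywhere, routine swabs to catch every symptom-free first infection, and a comparison that Section 13 does not specify.

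**What to change.** 1. Reconcile Table 1 and Section 11 with a sentence stating whether Section 11 screening continues after a first infection, so that Table 1 adds to it, or stops, so that Table 1 replaces it. Which testing rule applies is for the investigators to decide; the statistical need is that all sites follow the same one and that the two places agree.
2. Add a reason-for-test field (screening or symptoms) to the eCRF for every SARS-CoV-2 test.
3. For any analysis that compares first infection with reinfection, or uses prior infection as a predictor, count both on the same basis, for example symptom-triggered tests only, at least as a sensitivity analysis.

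The cost is a sentence and one extra eCRF field, and the reason for a test may be hard to recover later. The analysis on the common basis then describes symptomatic infection only.
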